- Presence of one or more of the following physiological states: systolic BP <90 mmHg, or MAP <65 mmHg, or increasing need for vasopressor drug infusion or pulse pressure variation >12 % or stroke volume variation >12%, or Cardiac index <2.2 L/min/m² or heart rate >100 or urinary output <20 ml/hr or either rising lactate levels or lactate levels >2 mmol/L or capillary refill time >3 seconds or central venous pressure <8 mmHg.

Exclusion criteria

- Confirmed or suspected pregnancy
- Patients with traumatic brain injury
- Active bleeding
- Haemoglobin level <70 g/L

• People who refuse blood products SWIPE Protocol UK V2.2, dated 18th May 2016 EudraCT No: 2016-001940, UK Protocol ID: R04336 • Patients in whom death is considered imminent (within 24 hours)

Sample size estimate

Given that in the first 48 hours the 5% albumin administered in the SAFE study [14] was a total of 1785ml (SD of 1865), we will aim to detect a decrease in fluid given to 1300ml (SD of 1368: proportionately the same as that seen in SAFE for a mean inout of 1785ml). This decrease of around 500ml in fluid input is considered of potential clinical value. To have a 90% power of detecting such a difference at an alpha level of 0.05, 195 patients will need to be randomised to each group. We have rounded this number up to 200 in each group to account for possible data loss.

Randomisation procedure

- Computer generated sets of random allocations will be produced by the Research Co-ordinator in advance of the study.
- Randomization will be by means of sealed envelopes with permuted blocks of variable size.
- Each envelope will contain a study arm allocation as well as a copy of a simplified version of the study protocol.
- Every patient who participates in any study related procedure will be assigned a unique patient number.

Intervention description

Patients will be randomised one of two arms:

• The treatment arm will receive an intravenous infusion of 20% albumin (Alburex

20®, CSL Behring, Marburg, Germany) every time the treating clinician decides SWIPE Protocol UK V2.2, dated 18th May 2016 EudraCT No: 2016-001940, UK Protocol ID: R04336 that a fluid bolus needs to be given during the first 48 hours in ICU. The treating clinician determines the volume and infusion rate of each fluid bolus.

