- Reason for admission to intensive care (post-operative complication, sepsis, medical emergency, post-operative management, other) and urgency (planned, unplanned, emergency). If surgical, date and type of operation.
- Weight and height on admission, to be used for calculation of body surface area.

Clinical Data

- Haemodynamic data: HR, ABP, CVP will be measured hourly during the study period.
- Blood gas results: PaO₂, lactate concentration, pH/H+ concentration, bicarbonate concentration, sodium concentration, chloride concentration, creatinine concentration, haemoglobin concentration and base deficit/excess will be measured hourly during the study period.
- Fluid balance Resuscitation fluids. Each fluid bolus will be recorded (type of resuscitation fluid, volume, infusion speed).

• Fluid balance – for each day or part there of. SWIPE Protocol UK V2.2, dated 18th May 2016 EudraCT No: 2016-001940, UK Protocol ID: R04336

- Baseline serum creatinine and urea pre-admission to ICU if available. Defined as
 a serum creatinine and urea taken in the six months pre-admission to hospital for
 this ICU event.
- Serum creatinine on admission, as indicated above, and as indicated clinically.
- Serum albumin on admission and as indicated clinically.
- Doses of furosemide administered (or rate of furosemide infusion).
- Doses of vasopressors and inotropes administered (or infusion rates).
- All other biochemical and haematological indices recorded as clinically indicated during the patient admission.

Outcome Data

- Primary efficacy outcome
 - Amount of resuscitation fluid (mL) administered over the first 48 hours in ICU.
- Secondary efficacy outcomes
 - The cumulative fluid balance after 48 hours in ICU.
 - The amount of vasoactive medication given over the first 4 hours after a fluid bolus and over the first 48 hours in ICU.
 - The total amount of fluids given over the first 4 hours after a fluid bolus,
 daily and over the first 48 hours in ICU.
 - The relative change in haemodynamic variables and blood gas results over the first 4 hours after a fluid bolus.
 - The relative change between baseline and peak creatinine in the first 48

hours after randomization.

- Patient-centred efficacy outcomes
 - Need for RRT
 - Renal status at 90 days
 - Hours on mechanical ventilation
 - ICU discharge status (alive or dead)
 - ICU length of stay
 - Hospital discharge status (alive or dead)

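### The 195 per group gives 90% power only at a one-sided 5% level that the protocol never declares; at two-sided 5%, the planned 200 per group gives about 84%

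*Protocol*

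**What the plan says.** The primary efficacy outcome (Outcome Data) is "Amount of resuscitation fluid (mL) administered over the first 48 hours in ICU".

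The Sample size estimate section takes the control figures from an earlier large albumin trial, in which the 48-hour volume "was a total of 1785ml (SD of 1865"). For the 20% arm it states: "we will aim to detect a decrease in fluid given to 1300ml (SD of 1368: proportionately the same" as in that trial. It adds: "This decrease of around 500ml in fluid input is considered of potential clinical value". It concludes: "To have a 90% power of detecting such a difference at an alpha level of 0.05, 195 patients will need to be randomised" (per group), and raises this to 200 for possible data loss.

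The paragraph does not give the sidedness of alpha. The Data analysis section lists a t-test or rank test for continuous outcomes, with log transformation where appropriate, and does not mention sidedness either. The Hypotheses section expects a lower volume with 20% albumin but does not define a one-sided rejection region.

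**The concern.** All the inputs to the calculation are printed, so the sample size can be checked directly. An alpha of 0.05 without qualification, for a two-group comparison of means, is conventionally read as two-sided. On that reading, 195 per group falls well short of 90% power.

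This is the protocol's only power statement, and it concerns the primary outcome. If testing is two-sided, the chance of missing a true 485 mL difference is about 16% rather than 10%, and a null result would be judged against a power that the trial did not have. If testing is one-sided, the reader is not told that the 90% depends on a criterion as lenient as a two-sided 10% test.

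**Working it through.** **Inputs** (Protocol, Sample size estimate): means 1785 and 1300 mL, difference 485 mL; SDs 1865 and 1368 mL; power 90%; alpha 0.05; equal groups.

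**Formula** (normal approximation, unequal SDs): n per group = (z_alpha + z_beta)² × (SD₁² + SD₂²) / difference².

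- SD₁² + SD₂² = 3,478,225 + 1,871,424 = 5,349,649
- difference² = 485² = 235,225
- ratio = 22.743

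**Step 1: reproduce the protocol's figure.** One-sided 5%: (1.6449 + 1.2816)² × 22.743 = 194.8, so 195. This matches exactly. An exact t-test calculation gives 196.

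**Step 2: two-sided 5%.** (1.9600 + 1.2816)² × 22.743 = 239.0 (238.97), so 239. The t-test gives 240. The planned 200 is 39 per group below this.

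**Step 3: power at the planned size.** The standard error is √(5,349,649 / n), and power is approximately Φ(485/SE − z_alpha).

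| n per group | SE (mL) | 485/SE | power, two-sided 5% | power, one-sided 5% |
|---|---|---|---|---|
| 195 | 165.6 | 2.928 | 83.4% | 90.0% |
| 200 | 163.5 | 2.965 | 84.3% | 90.7% |

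With the t distribution, the two-sided figures are 83.2% and 84.1%.

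**Step 4: difference detectable with 90% power at 200 per group, two-sided.** (1.9600 + 1.2816) × 163.5 = 530 mL.

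**Step 5: could another two-sided route lead to 195?** Per-group sizes for 90% power at two-sided 5%:

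| variant | n per group |
|---|---|
| difference 500 mL, both SDs | 225 |
| difference 485 mL, simple average of the SDs (1616.5) | 234 |
| SD 1865 in both arms, difference 485 or 500 mL | 311 or 293 |
| SD 1368 in both arms, difference 485 or 500 mL | 168 or 158 |
| rank test (239 / 0.955, or 239 × 1.15) | 250 to 275 |
| log scale, log-normal volumes | 155 |

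None is close to 195. Even with the rounded 500 mL difference, two-sided power at 200 per group is 86.4%.

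**Step 6: the second SD.** Scaling in proportion gives 1300 × 1865/1785 = 1358, where the protocol prints "1300ml (SD of 1368: proportionately the same as that seen in SAFE". With 1358, n becomes 194 (one-sided) or 238 (two-sided), a change of one patient per group.

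**Step 7: does the distribution matter?** Simulation with 200 per group, the protocol's means and SDs, and a two-sided 5% level (20,000 runs per shape):

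| assumed shape | raw-scale Welch t-test | t-test on logs |
|---|---|---|
| log-normal | 86% | 96% |
| gamma | 85% | about 65% |

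Raw-scale power stays close to the 84% of Step 3 under both shapes. Log-scale power depends heavily on the shape, which the protocol does not give.

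**The case against.** The strongest defence is that 195 is not a miscalculation. It follows exactly from the printed inputs at one-sided 5%, the protocol nowhere says two-sided, the paragraph speaks of detecting a decrease, and the hypothesis is directional. This stands in part: if a one-sided 5% test was intended, the 90% is correct. It does not remove the problem, because directional wording is used for nearly every endpoint in the Hypotheses section and does not amount to declaring a one-sided test. A SAP may settle the sidedness, but the power figure is printed in the protocol and needs its condition stated there.

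A reader might go further and infer that the power fails for the test that will be reported. The documents do not support that, because they do not fix the sidedness of that test. The chi-square and log-rank tests in the Data analysis section do not help: they are assigned to categorical data and to in-hospital mortality and discharge home, not to fluid volume.

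A reader might also infer that the trial is too small. Power of 84% exceeds the common 80% target. The protocol calls its 400 patients a convenience sample, puts feasibility among its first aims and describes its physiological findings as pilot. The Background reports a five-fold volume difference in an observational study, far larger than the planned reduction of 485/1785 = 27%. Type I error, the estimate and its confidence interval are unaffected. These points limit the seriousness but do not make the 90% correct under a two-sided reading.

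Finally, a reader might expect log transformation to restore the power. It gives 96% only if volumes are log-normal; with gamma-shaped volumes of the same means and SDs it gives about 65%.

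**Conclusion.** The power statement is wrong as written under the conventional reading of its alpha. The stated 195 reproduces only at one-sided 5%, which the protocol does not declare. At two-sided 5%, 90% power needs 239 per group, and the planned 200 gives about 84% (about 83% if losses leave 195).

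These figures rest on the protocol's own means and SDs, equal allocation and a comparison of means on the raw scale. The conclusion is conditional: if a one-sided 5% test was intended, the arithmetic is right and the fault is that this was not stated. The SD slip (1368 for 1358) is real but immaterial. The paragraph should be fixed, but this is a correction of wording and does not show that the trial is inadequately sized.

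**What to change.** State the sidedness of the primary test in the Sample size estimate section and make the power figure agree with it.

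- **If two-sided**, suggested wording: *With 200 patients per group and a two-sided 5% test, power is 84% for a difference of 485 mL, and 90% for a difference of 530 mL.* Add that power is about 83% if data loss leaves 195 per group.
- **If one-sided 5% is truly intended**, declare it explicitly for the primary analysis, so that the 90% can be read correctly.

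In either case, correct the SD for the 20% arm to 1358 mL; this changes the calculated size by one per group. Do not add patients, and do not cite a log-scale analysis as the justification for the sample size.

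The cost is a change of protocol wording. Under the two-sided choice the stated power becomes somewhat less favourable; recruitment, design and patient care do not change.

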Albumin is a natural constituent of human blood with a high capacity of binding water. In the United Kingdom, two different albumin-containing solutions are widely and routinely used for fluid resuscitation; a 5% solution (containing 50 mg albumin per ml) and a concentrated 20% solution (containing 200 mg albumin per ml). Theoretically, the concentrated 20% albumin solution can accomplish the same volume expansion effect as the 5% solution using only one fifth of the administered volume. A reduced volume of fluid administered may ultimately attenuate the severity of organ damage, expedite recovery from the critical illness and reduce mortality. This study is an investigator-initiated, multi-centre, open label, randomised-controlled trial. In the UK, the study has been determined to be a Clinical Trial of an Investigational Medicinal Product by the Competent Authority. The aim of this study is to test whether fluid resuscitation with the 20% albumin solution reduces fluid accumulation and organ damage in critically ill patients as compared to fluid resuscitation with the 5% albumin solution. The study will enrol a convenience sample of 400 adult participants. These patients will be recruited across three intensive care units in Melbourne and Adelaide, Australia and Manchester in the United Kingdom. We intend to publish aggregated findings in peer-reviewed critical care journals.

Background

Intravenous fluid administration is an integral part in the treatment of hemodynamic instability. The rationale for fluid therapy is to increase intravascular volume, venous return and cardiac output with the aim to improve perfusion and oxygen delivery to the organs. There is, however, considerable clinical controversy about the optimal use of fluids (type and extent) to achieve and maintain hemodynamic stability. Evidence from multiple observational studies, however, suggests that a prolonged and uncritical fluid therapy is, by causing fluid accumulation and tissue oedema, associated with the development and progression of organ failure and increased mortality in critically ill patients [1].

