The control arm will receive an intravenous infusion of 5% albumin (Alburex 5[®], CSL Behring, Marburg, Germany) every time the treating clinician decides that a fluid bolus needs to be given during the first 48 hours in ICU. The treating clinician determines the volume and infusion rate of each fluid bolus.

Randomised participants in this study will receive and infusion of 20% albumin (treatment group) or 5% albumin (control group) each time the treating physician decides that a fluid bolus needs to be given during the first 48 hours of ICU. The treating clinician determines the volume and infusion rate of each bolus. Other fluids (nutrition, drug infusions, blood products) are given as per the discretion of the treating clinician.

Blinding

Blinding in this trial is not possible as Alburex $20^{\$}$ comes in 100 mL glass bottles whereas Alburex $5^{\$}$ comes in 500 mL bottles.

Monitoring

- Routine clinical monitoring shall continue after recruitment to the study.
- Routine monitoring of critically ill patients admitted to the ICU includes:
 - Heart rate (HR)
 - Arterial blood pressure (ABP)
 - Central venous pressure (CVP)

Oxygen saturation (SpO₂)
 SWIPE Protocol UK V2.2, dated 18th May 2016
 EudraCT No: 2016-001940, UK Protocol ID: R04336

- Urine output (UO)
- Respiratory rate (RR)
- Temperature
- o Fluid intake
- Fluid output
- Ventilator settings
- Blood gas results
- Serum creatinine
- Serum albumin

Patient Care

- Participation in the study shall not affect patient treatment in any other way.
- All additional therapies shall be administered at the discretion of the treating clinician.
- These therapies include:
 - Oxygen therapy
 - Antibiotics
 - Radiological investigations
 - Surgical interventions

There will be no attempt to control any other treatment. In particular there will be no attempt to control vasopressor therapy, oxygen therapy, antibiotics, blood, blood products and surgical intervention.

Data collection

The case report form will collect the information detailed below. The electronic medical records and previous volumes of notes will be accessed to collect baseline data where appropriate. Laboratory data will be accessed to acquire the items detailed below. We will perform a data review after the first 20 patients to ensure our data capture strategy is appropriate.

Data will be collected on the following variables:

Patient data

- Code for patient, gender and age. Date of admission to ICU and to hospital.

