 - Hospital outcome (discharge destination home, another hospital, advanced care institution)
 - Hospital length of stay (date of discharge)
 - Mortality status at 90 days.
- Feasibility and safety outcomes:
 - Distribution of values for primary and secondary outcome
 - Randomized / Screened patients ratio
 - Data completion rate
 - Loss to follow-up rate
 - Recruitment rate and duration
 - Separation in amount of fluid given

Safety outcomes

- Development of side-effects
- Episodes of hypotension
- Development of kidney failure

o Adverse changes in any of the physiological efficacy measures

Data analysis

Outcomes will be compared after log transformation where appropriate. Comparisons will be made using t-test and ANOVA for repeated-measures or Wilcoxon rank-signed test and Kruskall-Wallis according to the underlying distribution for continuous data and Chi-square for categorical data. A Kaplan-Meier curve with log-rank test will be performed to further compare in-hospital mortality and rate of discharge home. Logistic regression analysis will also be performed to adjust for baseline imbalances. Analysis will be an on intention-to-treat basis.

Risks and Benefits

Albumin solutions have been used for resuscitation since the 1940s. An investigation of the safety of albumin solutions showed that between 1998 and 2000, approximately 10⁷ units of such albumin solutions were administered worldwide. Adverse effects that were directly associated with albumin were an extremely rare event during this observation period [15]. There are, however, more recent reports that the use of (20%) albumin is associated with increased mortality for patients with traumatic brain injury [6]. Accordingly, patients with traumatic brain injury will be excluded from the SWIPE study. Although albumin is prepared from pooled plasma, albumin preparations currently available are considered to be non-allergenic due to the manufacturing process.

Data handling, retention, storage and destruction

Data handling

The case report form (CRF) will be developed by the members of the investigator team as a paper CRF. All data will be collected by members of the investigator team as described in the CRFs from the source data. Information recorded in the CRF should accurately reflect the subject's medical/hospital notes and must be completed as soon as it is made available.

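### The protocol does not say whether each of the three ICUs has its own blocked sequence, and its named comparisons leave site out although local clinicians determine the primary outcome

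*Protocol*

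**What the plan says.** The Randomisation procedure section gives the whole allocation rule. On the lists: "Computer generated sets of random allocations will be produced by the Research Co-ordinator in advance of the study". On the method: "Randomization will be by means of sealed envelopes with permuted blocks of variable size". No stratification factor is named, and nothing says whether a set belongs to one hospital or is shared.

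The opening summary says that patients will be "recruited across three intensive care units in Melbourne and Adelaide, Australia and Manchester in the United Kingdom". The Publication section speaks of two study sites, so the document is not consistent on the site structure.

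The Intervention description leaves bolus volume to the bedside in both arms: "The treating clinician determines the volume and infusion rate of each fluid bolus". The primary efficacy outcome is "Amount of resuscitation fluid (mL) administered over the first 48 hours in ICU".

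The Data analysis section opens with "Comparisons will be made using t-test and ANOVA for repeated-measures", with rank tests as the alternative. Site appears nowhere in it. The only adjustment named is logistic regression, which does not fit a continuous volume.

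**The concern.** The endpoint is the sum of decisions made by local clinicians. They decide when a bolus is needed and how large it is, and the protocol makes no attempt to control other treatment. Three units in two countries may well differ in how freely they give fluid, so site is an obvious prognostic factor for this outcome. Neither the allocation rule nor the analysis deals with it.

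There are two possible readings of the allocation rule, and each has its own consequence.

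- **Separate sets per ICU.** The trial is stratified by site, but the stated t-test treats the data as unstratified. Between-site variance stays in the error term although the design has removed it from the arm difference. The standard error is too large and the test is conservative.
- **One shared list.** Balance within a site is not assured. Chance differences in site mix add random noise to the arm difference.

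What is at stake is precision, not validity.

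**Working it through.** **Inputs from the Sample size estimate section.** Control mean 1785 mL, SD 1865; treatment mean 1300 mL, SD 1368; difference 1785 − 1300 = 485 mL; alpha 0.05, sidedness not stated; power 90%; 195 per arm, rounded up to 200.

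**Assumption.** The share of outcome variance due to site, ρ, is not in the document. I use 0.01 to 0.10 and hold the total SD fixed. For three equal sites spaced d mL apart, the between-site variance is (2/3)d², so this range corresponds to d from about 200 to about 633 mL.

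**Step 1. Reproduce the plan's figure.** Average variance = (1865² + 1368²)/2 = 2,674,824.5, so the SD is 1635.5 mL. With n = 2(z_α + z_β)² × variance / 485²:

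- one-sided: 2 × (1.645 + 1.282)² × 2,674,824.5 / 235,225 gives 195, which matches;
- two-sided: 2 × (1.960 + 1.282)² × 2,674,824.5 / 235,225 gives 239, which does not match.

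Both versions are therefore carried forward.

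**Step 2. Power without a site term, 200 per arm.** Standard error = 1635.5 × √(2/200) = 163.5 mL, and 485/163.5 = 2.966.

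- Two-sided: Φ(2.966 − 1.960) = 84.3%.
- One-sided: Φ(2.966 − 1.645) = 90.7%.

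**Step 3. Power with site balanced and in the model.** The standard error becomes 163.5 × √(1 − ρ).

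| ρ | Standard error (mL) | Two-sided power | One-sided power |
|---|---|---|---|
| 0 | 163.5 | 84.3% | 90.7% |
| 0.01 | 162.7 | 84.6% | 90.9% |
| 0.02 | 161.9 | 85.0% | 91.2% |
| 0.05 | 159.4 | 86.1% | 91.9% |
| 0.10 | 155.2 | 87.8% | 93.1% |

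**Step 4. Sets per site, but the t-test as written.** The reported standard error exceeds the true one by the factor 1/√(1 − ρ), which is 1.005 at ρ = 0.01 and 1.054 at ρ = 0.10. The actual two-sided error rate is 2[1 − Φ(1.960/√(1 − ρ))], about 4.9% and 3.9%. Power is Φ((485 − 1.960 × 163.5)/(163.5 × √(1 − ρ))), about 84.4% and 85.5%. On this reading the site term itself adds about 0.2 to 2.3 points.

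**Step 5. One shared list.** If patients at all sites draw from it in order of arrival, the chance shift in the arm difference has an SD of about 163.5 × √ρ: 23, 37 and 52 mL at ρ = 0.02, 0.05 and 0.10. A 5,000-run simulation (block sizes 2, 4 and 6 assumed) agrees: 23, 36 to 37 and 51 to 52 mL, with a mean of about zero. If the list is instead dealt out in consecutive runs of envelopes, only the blocks at the boundaries are broken. With assumed site means of 1200, 1800 and 2700 mL and 170, 130 and 100 patients, the SD is then about 6 mL.

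**The case against.** **The protocol may already randomise by site.** It speaks of sets in the plural, issued as paper envelopes to hospitals in two countries, which fits one set per ICU. This stands. A reader might infer that randomisation is not by site, but the text does not say so. It only fails to say which applies.

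**The chance imbalance is ordinary sampling error.** This also stands. A reader might infer that site imbalance biases the primary result or shifts it by a large amount. Under the assumed means in step 5, an interleaved list gives a shift with an SD of about 60 mL and a 95th percentile of 117 mL. But those means put 13% of the variance between sites (354,600 / 2,674,824.5), above the range used here, and the figure needs patients at all ICUs to draw one by one from a single list. Even then the shift averages zero and is already part of the 163.5 mL standard error of an unstratified trial. It causes no bias and no excess type I error.

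**A site term belongs in the SAP.** An SAP may exist and may add one. This answers only part of the point. The protocol itself names unadjusted tests for its comparisons, and the lists are made before the study starts, so a later SAP cannot change how patients were allocated.

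**Conclusion.** The point holds as a gap in the allocation rule together with an analysis that leaves out an obvious prognostic factor. It is a recommended improvement and does not threaten the primary result. Over an assumed site share of 1% to 10%, stratifying and adjusting adds about 0.3 to 3.5 points of two-sided power, or 0.2 to 2.4 points of one-sided power, at 200 per arm. Most of that comes from the site term: stratifying without adjusting only makes the test conservative. The size rests wholly on the assumed share, because the document gives no between-site variance. The unstated sidedness of alpha costs more power (90.7% against 84.3%) and is a separate matter.

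**What to change.** - In the Randomisation procedure section, state that each ICU has its own computer-generated sequence in permuted blocks of variable size. If recruitment has begun under another arrangement, describe what was done.
- In the Data analysis section, include site as a fixed effect in the primary and secondary comparisons, or as the stratum where a rank test is used.
- Reconcile the three ICUs in the summary with the two study sites in the Publication section, so that the number of strata is clear.

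The cost is three lists in place of one and two degrees of freedom out of about 398. No extra patients or data are needed.

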We recently found, in an observational study, that patients resuscitated with the diluted 5% albumin solution received five times more volume compared to patients resuscitated with the concentrated 20% albumin solution [11]. Despite this difference, a trend towards higher mean arterial blood pressure up to four hours after a bolus of 20% albumin (compared to a bolus of 5% albumin) was seen (P = 0.056, Figure 1). In addition, more patients receiving 5% albumin needed further fluid boluses within 24 hours as compared to patients receiving 20% albumin (58% versus 45%, P = 0.049). Finally, patients resuscitated with concentrated 20% albumin received approximately 30 times less chloride than those in the 5% albumin group. This is an important SWIPE Protocol UK V2.2, dated 18^{th} May 2016 EudraCT No: 2016-001940, UK Protocol ID: R04336

finding since administration of chloride-rich solutions is associated with more complications, including severe renal failure requiring dialysis [12, 13].

Figure 1. Mean arterial blood pressure over the first four hours following a fluid bolus of either 100 mL, 20% albumin solution or 500 mL, 5% albumin solution, including baseline values at 0 hours.

Aims

The aim of this study is to establish the feasibility, safety, biochemical and physiological efficacy of 20% albumin compared with 5% albumin for fluid bolus therapy in critically ill patients.

Specifically, we aim to study the effect of intravenous 20% albumin infusion compared to 5% albumin infusion on the following variables:

- Mean arterial blood pressure (first 4 hours)
- Central venous pressure (first 4 hours)
- Cardiac output (first 4 hours)
- Urinary output (first 4 hours)
- Serum biochemistry (first 4 hours)

- Volume of fluid administered over the first 4 hours and first 48 ICU hours following recruitment
- Use of vasoactive medications over the first 48 ICU hours following recruitment
- Serum chloride levels over the first 48 ICU hours following recruitment
- Serum albumin levels over the first 48 ICU hours following recruitment
- Renal function based on changes in serum creatinine and urine output in the first 48 ICU hours.
- Lung function based on arterial partial oxygen pressure (PaO₂)/fraction of inspired oxygen (FiO₂) ratio in the first 48 hours in ICU

Hypotheses

- We hypothesise that the administration of 20% albumin for fluid resuscitation in critically ill patients will be feasible and safe when compared to administration of 5% albumin

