- We hypothesise that a lower volume of resuscitation fluid will be administered over the first 4 and 48 hours in ICU in patients receiving 20% albumin than in patients receiving 5% albumin.
- We hypothesise that the cumulative fluid balance over the first 48 hours in ICU will be significantly lower in patients receiving 20% albumin than in patients receiving 5% albumin.
- We hypothesise that the administration of 20% albumin will create a significantly greater increase in the hourly and mean arterial blood pressures over the study period compared to the 5% albumin.

- We hypothesise that the mean central venous pressure will be significantly lower in patients receiving 20% albumin than in those patients receiving 5% albumin.
- We hypothesise that patients receiving 20% albumin will require less vasoactive medications over the study period as compared to patients receiving 5% albumin.
- We hypothesise that the overall administration of chloride will be less in patients receiving 20% albumin than in patients receiving 5% albumin.
- We hypothesise that 20% albumin administration will significantly reduce peak serum creatinine in the first 48 hours following randomisation when compared to 5% albumin administration.
- Finally, we hypothesise that the administration of 20% albumin will significantly increase the PaO₂/FiO₂ ratio when compared to the administration of 5% albumin.

Relevance and Importance

- The association between fluid accumulation and poor patient outcomes has been established.
- Fluid resuscitation with 20% albumin may reduce the volume of fluid administration.
- A reduced volume of fluid administered during critical illness may achieve similar hemodynamic improvements without the need for additional volume administration

Methodology

Study design

The SWIPE study is an investigator-initiated, multi-centred, open label, randomisedcontrolled trial.

Participant recruitment and selection

All patients will be recruited if they meet the inclusion criteria and no exclusion criteria.

Inclusion criteria

- Admitted to the intensive care unit at participating sites for less than 24 hours.
- Age 18 years or greater
- Need for fluid bolus as determined by the treating clinician

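### The primary fluid volume has two conflicting time origins, and the one in the outcome definition takes in fluid given before randomisation

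*Protocol*

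**What the plan says.** The Protocol dates the fluid volume in two ways.

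- **From ICU admission.** The primary efficacy outcome under Outcome Data is "Amount of resuscitation fluid (mL) administered over the first 48 hours in ICU". The Hypotheses match it: "a lower volume of resuscitation fluid will be administered over the first 4 and 48 hours in ICU". Under Intervention description, study fluid is given each time the clinician decides "that a fluid bolus needs to be given during the first 48 hours in ICU".
- **From recruitment.** The Aims list "Volume of fluid administered over the first 4 hours and first 48 ICU hours following recruitment".

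The Inclusion criteria require that a patient be "Admitted to the intensive care unit at participating sites for less than 24 hours", so up to almost 24 hours in ICU can pass before randomisation. No sentence removes fluid given in that interval from the outcome.

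The Protocol uses a randomisation origin elsewhere. The creatinine hypothesis is that 20% albumin will "reduce peak serum creatinine in the first 48 hours following randomisation", and the matching secondary outcome is also dated from randomisation. Cumulative fluid balance, 48-hour total fluids and 48-hour vasoactive dose are dated from ICU admission under Outcome Data, although the Aims date vasoactive use from recruitment.

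**The concern.** Fluid given before allocation cannot respond to allocation. If it is counted, part of each patient's total is the same in expectation in both arms, so the proportional difference shrinks and variation in earlier care is added to the error. A fixed stop at ICU hour 48 also means that a late entrant has as little as 24 hours in which the allocated fluid can act.

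This affects the sole primary outcome. The other outcomes on the ICU clock (cumulative fluid balance, total fluids, vasoactive dose) share the fault. It is more than a detail left to the analysis plan: the Protocol fixes the window in two incompatible ways, and an analysis plan would have to override one of them. Separating the fluid afterwards is not assured either. The Clinical Data list names the type, volume and infusion speed of each bolus, but not its time or the time of randomisation.

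**Working it through.** **Inputs from the Sample size estimate:** means 1785 and 1300 mL, SDs 1865 and 1368 mL, power 90%, alpha 0.05 with no side stated, 195 per group rounded up to 200.

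**Step 1: the Protocol's own figure.**
- Difference: 1785 − 1300 = 485 mL, or 485/1785 = 27%.
- Root-mean-square SD: √[(1865² + 1368²)/2] = 1635.5 mL.
- n per group = 2 × SD² × (z_alpha + z_beta)² / difference².
- One-sided 5%: 2 × 1635.5² × (1.645 + 1.282)² / 485² = 195, as stated.
- Two-sided 5%: the same with 1.960 in place of 1.645 gives 239.

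The stated 195 reproduces only as a one-sided test. That is a separate matter, so both versions are carried forward to keep the two losses apart.

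**Step 2: the dilution.** Let f be the share of the 48-hour ICU fluid given before randomisation. The Protocol does not give f. Assumptions: 1785 mL is the control total over the ICU-based window, the planned 27% reduction acts only on fluid after randomisation, the SDs stay as planned, and 200 per group are analysed. Then

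- difference = 485 × (1 − f)
- standard error = 1635.5 × √(2/200) = 163.5 mL
- power = Φ(difference/163.5 − z_alpha)

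| f | Difference (mL) | Power, two-sided | Power, one-sided |
|---|---|---|---|
| 0 | 485 | 84% | 91% |
| 0.10 | 436.5 | 76% | 85% |
| 0.25 | 364 | 60% | 72% |
| 0.50 | 242.5 | 32% | 44% |

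For scale, at a constant fluid rate a patient randomised at ICU hour t has f = t/48. That gives 0.25 at 12 hours and 0.50 at 24 hours. The last row would need every patient to enter at the limit, so it is an extreme bound.

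If the SD in the 20% arm is scaled with its mean, two-sided power at f = 0.25 is 58% instead of 60%.

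**Step 3: the other reading of 1785 mL.** The Protocol does not say where the 48 hours behind that figure begin. If it is fluid given after allocation, what is lost from the treated total is only the part falling after ICU hour 48. Assume entry spread evenly over 0 to 24 hours and a need for fluid that halves every 12 hours after entry:

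- The share of need arising within 48 hours of entry is 1 − 0.0625 = 0.9375.
- The average share arising before ICU hour 48 is 1 − (0.25 − 0.0625)/(24 × 0.0578) = 0.865.
- The ratio is 0.865/0.9375 = 0.92, so about 8% is lost.
- The difference is 485 × 0.92, about 447 mL, and two-sided power is about 78%, before any variance added by pre-entry fluid.

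The smaller loss depends on need falling after entry. With a constant rate and the same spread of entry, the mean loss would be 12/48 = 25% on this reading too.

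**The case against.** **The contradiction may be only loose wording.** Recruitment and randomisation are nearly the same moment, so there are two origins and not three, and the Aims already hold the sensible one. This stands as far as it goes. The defect is an inconsistency, not a design the sponsor clearly chose. But the definition labelled primary is the ICU-based one, and the same list dates creatinine from randomisation, so a reader must take the clocks as different.

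**The power figures rest on an unknown f.** This stands. Entry requires a current need for a bolus plus a physiological trigger, and enrolment without prior consent is allowed. Both are compatible with early entry and with fluid concentrated after it. Neither proves a small f.

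**A reader might infer that the comparison is biased.** The Protocol does not support that. Pre-randomisation fluid has the same expectation in both arms, so the intention-to-treat comparison remains valid.

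**A reader might also infer that sites will report different quantities.** That is possible with two definitions in force, but nothing shows it, and a data-capture review is planned after the first 20 patients.

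**Simply starting a 48-hour outcome at randomisation would cause a new mismatch.** This stands. As written under Outcome Data and Intervention description, the outcome window and the study-fluid period both stop at ICU hour 48. Moving only the outcome would add up to 24 hours in which study fluid is not specified.

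**Conclusion.** The point holds as an inconsistency with a real cost. The Aims conflict with the Hypotheses and Outcome Data on where the primary quantity begins, and the outcome as defined admits fluid that allocation cannot affect. The harm is dilution and lost precision, not a tilt towards either arm.

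The wording conflict is certain; the size of the loss is not. Under the Step 2 assumptions, even f = 0.10 takes power at 200 per group below the planned 90% on either sidedness. The loss is smaller than the table shows if 1785 mL already refers to fluid after randomisation and need falls after entry. It would be wrong to say that the trial has 60% power. That figure belongs to one assumed f and a two-sided test, and 84% is the two-sided starting point even with no dilution.

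**What to change.** - Define the primary outcome, and the related fluid-balance, total-fluid and vasoactive outcomes, to count only what is given after randomisation, with one stated origin used throughout.
- Record the time of randomisation and the time of each bolus. Record resuscitation fluid given in ICU before randomisation and use it as a baseline covariate.
- Reconcile the outcome window (Aims, Hypotheses, Outcome Data) with the study-fluid period (Intervention description) so that the two end together. How long the study-fluid period lasts is for the sponsor to decide. A count that starts at randomisation and stops when that period stops would meet this requirement at any length.

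The cost is changed outcome wording and a few case report form fields, plus a protocol amendment to the treatment schedule if the sponsor alters the study-fluid period. No extra patients are needed.
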